
### **13.9 Interim Analysis**

None planned.

### **13.10 Ancillary Studies**

None planned.

## **14. ETHICAL AND REGULATORY CONSIDERATIONS**

### **14.1 Form FDA 1572**

Prior to initiating this study, the Protocol Lead Investigator at the Lead or Participating Organization(s) will provide a signed Form FDA 1572 stating that the study will be conducted in compliance with regulations for clinical investigations and listing the investigators, at each site that will participate in the protocol. All personnel directly involved in the performance of procedures required by the protocol and the collection of data should be listed on Form FDA 1572.

### **14.2 Other Required Documents**

14.2.1 Current (within two years) CV or biosketch for all study personnel listed on the Form FDA 1572 and Delegation of Tasks form for the Lead Organization and all Participating Organizations. CVs or biosketches do not need to be updated for participating study staff after drug shipment authorization (DSA). “

14.2.2 Current medical licenses (where applicable) for all study personnel listed on Form FDA 1572 and Delegation of Tasks form for the Lead Organization and all Participating Organizations.

14.2.3 Lab certification (*e.g.*, CLIA, CAP) and lab normal ranges for all labs listed on Form FDA 1572 for the Lead Organization and all Participating Organizations.

14.2.4 Documentation of Good Clinical Practice training for all study personnel listed on the FDA Form 1572 and Delegation of Tasks form for the Lead Organization and all Participating Organizations.

14.2.5 Documentation of Federalwide Assurance (FWA) number for the Lead Organization and all Participating Organizations.

14.2.6 Signed Investigator’s Brochure/Package Insert acknowledgement form

14.2.7 Delegation of Tasks form for the Lead Organization and all Participating Organizations signed by the Principal Investigator for each site and initialed by all study personnel listed on the form

14.2.8 Signed and dated NCI, DCP Financial Disclosure Form for all study personnel listed on Form FDA 1572 for the Lead Organization and all Participating Organizations

### **14.3 Institutional Review Board Approval**

Prior to initiating the study and receiving agent, the Investigators at the Lead Organization and the Participating Organization(s) must obtain written approval to conduct the study from the Central IRB. Should changes to the study become necessary, protocol amendments will be submitted to the DCP PIO

according to DCP Amendment Guidelines. The DCP-approved amended protocol must be approved by the Central IRB prior to implementation

#### **14.4 Informed Consent**

All potential study participants will be given a copy of the Central IRB-approved Informed Consent to review. The study coordinator will explain all aspects of the study in lay language and answer all questions regarding the study. If the participant decides to participate in the study, he/she will be asked to sign and date the Informed Consent document. The study agent(s) will not be released to a participant who has not signed the Informed Consent document. Subjects who refuse to participate or who withdraw from the study will be treated without prejudice.

Participants must be provided the option to allow the use of blood samples, other body fluids, and tissues obtained during testing, operative procedures, or other standard medical practices for further research purposes. If applicable, statement of this option may be included within the informed consent document or may be provided as an addendum to the consent. A Model Consent Form for Use of Tissue for Research is available through a link in the DCP website.

Prior to study initiation, the informed consent document must be reviewed and approved by NCI, DCP, the Central IRB, the Consortium Lead Organization, and the IRB at each Organization at which the protocol will be implemented. Any subsequent changes to the informed consent must be approved by NCI, DCP, the Central IRB, and then submitted to each organization's IRB for approval prior to initiation.

#### **14.6 Other**

This trial will be conducted in compliance with the protocol, Good Clinical Practice (GCP), and the applicable regulatory requirements.

## **15. FINANCING, EXPENSES, AND/OR INSURANCE**

All research related costs associated with participating in this study will be paid for, and will not be the responsibility of the participant. However, it is possible that injury may result from participating in this study. Any expenses incurred as a result of research related injury will be the responsibility of the study participant and/or their insurance carrier.

**APPENDIX A**  
**Performance Status Criteria**

**ECOG Performance Status Scale**

Grade	Descriptions
0	Normal activity. Fully active, able to carry on all pre-disease performance without restriction.
1	Symptoms, but ambulatory. Restricted in physically strenuous activity, but ambulatory and able to carry out work of a light or sedentary nature (e.g., light housework, office work).
2	In bed <50% of the time. Ambulatory and capable of all self-care, but unable to carry out any work activities. Up and about more than 50% of waking hours.
3	In bed >50% of the time. Capable of only limited self-care, confined to bed or chair more than 50% of waking hours.
4	100% bedridden. Completely disabled. Cannot carry on any self-care. Totally confined to bed or chair.
5	Dead.

**Karnofsky Performance Scale**

Percent	Description
100	Normal, no complaints, no evidence of disease.
90	Able to carry on normal activity; minor signs or symptoms of disease.
80	Normal activity with effort; some signs or symptoms of disease.
70	Cares for self, unable to carry on normal activity or to do active work.
60	Requires occasional assistance, but is able to care for most of his/her needs.
50	Requires considerable assistance and frequent medical care.
40	Disabled, requires special care and assistance.
30	Severely disabled, hospitalization indicated. Death not imminent.
20	Very sick, hospitalization indicated. Death not imminent.
10	Moribund, fatal processes progressing rapidly.
0	Dead.

**APPENDIX B**  
Diary and instructions for gel use

**Study Diary Part I**

Protocol Number

Subject ID

Site

Name

Start date

End Date

Dear research participant,

Thank you for participation in this study. It is important that you fill in the diary every day and bring it with you to your visit just before your surgery. If you do not have the diary with you, continue to record information on note paper and copy it onto the diary afterwards. If you lose the diary, please contact the study staff immediately to get another diary.

Please remember to apply the gel every morning. Each canister should be used for only 40 days (even if some gel remains). Your cooperation in this study is greatly appreciated. Bring all canisters back with you at your next visit, whether gel remains in the canister or not.

Canister #1	Date of first use	Date of last use
Canister #2	Date of first use	Date of last use

---

Study Coordinator's Signature/Date

**Study Diary Part II**

Protocol Number  
Subject ID  
Site

Name  
Start date

End Date

Day	Monday	Tuesday	Wednesday	Thursday	Friday	Saturday	Sunday
Date							
Time							
How many hot flashes in the past 24 hours above your normal experience?	0 1-5 6-10 11-15						
Night sweats in the past 24 hours above your normal experience?	Yes No						
Did you apply your gel to both breasts, a total of 2 complete pumps (1 complete pump per breast?)	Yes No						
Did you discard any pumped doses of gel?	Yes No						
If yes, how many pumped doses did you discard?							
Did you take your capsule?	Yes No						
Are you having a period?	Yes No						

Study Coordinator's Signature/Date

To be repeated, for each week, until end of intervention

### **GEL APPLICATION INSTRUCTIONS:**

1. Flammable: do not apply near fire, flame or heat, or while smoking
2. Apply the gel to your own breasts after bathing, preferably in the morning and at approximately the same time each day.
3. To apply, remove the cap from the canister. When you use a canister for the first time, you must prime it by pressing the pump fully several times until gel is dispensed (point the spout toward a sink or wastebasket and do not use the first dose, which may be incorrect).
4. Once the canister is primed, hold it in one hand and place the palm of your other hand under the pump to catch the gel. Be sure to press down completely on the pump and release it completely to dispense one dose of gel.
5. Apply **one dose of gel to each breast** (dosage is indicated on the canister label). Do not apply more or less than one dose to each breast. Be sure to release the pump completely between both actuations.
6. If you accidentally pump twice for one breast, please discard this dose and try again to get one pump. If you do discard pumped doses, please record this on your study diary Part II
7. Spread the gel evenly over the entire surface of your breast, without rubbing.
8. Wash your hands immediately after applying the gel.
9. Allow the gel on your breasts to air dry for 2 minutes and then immediately cover with clothing (the gel is colorless and will not stain your clothing). Once dry, the gel is no longer flammable. Do not expose your bare breasts to sunlight at any time.
10. Do not apply any other cream, lotion or moisturizer to your breasts at any time during the study.
11. Do not wash your breasts or immerse in water (bath, swim) for at least 4 hours following application of the gel. If this is not possible, delay application of the gel that day until after immersion, and be sure to follow all the above instructions. If you regularly swim in the morning, it is better to apply the gel afterwards, after your shower.
12. After use, replace the cap on the canister.
13. Switch to a new canister of gel every 40 days.

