## **5.7 Adherence/Compliance**

5.7.1 Participants will be considered compliant if they have taken 80% of the prescribed doses and have missed no more than 3 doses in the final 14 days prior to surgery.

5.7.2 The participants will be asked at registration if they would like to utilize a phone application in place of paper forms. According to subject preference, participants will either utilize phone application or fill out paper forms daily to monitor compliance. For participants utilizing the phone application, the study coordinator will be notified after 2 days of missed entries. For individuals using paper forms, email messages will be sent daily for the first week; in following weeks, messaging will be targeted to women having difficulty remembering their dose.

5.7.3 Capsule counts and weighing of gel dispensers will be performed at the conclusion of therapy. Drug and metabolite levels will be measured in blood and tissue on the last day of administration. Prescribed doses include one capsule per day, or one pump of the gel on each breast per day. If the capsule count consumed by the subject is lower than  $D*80\%$ , or the amount of gel consumed is less than  $2D*80\%*[m - sd(m)]$ , where D is the number of days between visits, m and  $sd(m)$  are the mean and standard deviation of the weight of one pump of the gel provided by the manufacturer, or if more than three doses of therapy are missed during the final 14 days, the subject will be considered non-compliant. For subjects with only one breast, the lower limit of the amount of gel consumed for compliance is  $D*80\%*[m - sd(m)]$ . All participants who receive a study agent for any period of time will be evaluable for toxicity. Treatment compliance assessment will be based on the active ingredient component of the treatment regimen, i.e. the pill count for the Oral Tamoxifen group and gel dispenser weight for the 4-OHT gel group.

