Agent will be supplied in a kit. Each kit contains two canisters of 4-OHT/ placebo gel and one bottle of 120 tamoxifen/placebo capsules. Each kit will have a label printed with the treatment kit number, protocol number and contents and storage temperature along with the statement “Caution: New Drug- Limited by Federal law (US) to investigational use”. Each kit (and its contents) will be labelled so that any oral active kit or any gel active kit can be given to any participant. The portion of the label indicating placebo or active drug will be removed by the pharmacy when the kit is dispensed. The pharmacy will attach pre-printed label overlays with the randomization number of the subject receiving the study drug, and canisters numbers provided by MRI Global. Dispensing pharmacist shall open the kit, affix prescription labels to both capsule bottles and dispensers with written direction according to the prescribing instruction. Fill out blank sections on the bottles and dispensers indicating subject number and subject initials. Weigh all dispensers and record final gross weight on the space provided on the dispenser itself and on the form. Detach peel-off label from each kit and affix it to the form, which is kept in the study binder. Pharmacies that use an eDARF shall print out the logs from their electronic accountability system upon request and keep the logs in the study binder.

The kit will be given/shipped to the patient at the time of randomization and collected at Study Visit 1. If the kit is shipped to participant, the pharmacy or coordinator will package the supplies at controlled room temperature. Please see the NWU2015-06-04 pharmacy manual for shipping procedures and specifications.

Placebo gel will be packaged into canisters for the purpose of demonstration. These canisters are labeled “For demonstration purposes only” and provided to study coordinators to show consented participants how to pump the canister and what the gel looks like. Participants are allowed to touch the gel and are asked to wash their hands after the demonstration.

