
**Adverse Events.** AEs will be assessed using CTCAE. Worst grade toxicity for each AE type will be summarized by arm using descriptive statistics. For each AE type, proportions of patients experiencing toxicity of any grade will be compared between arms using Fisher's exact test.

**Treatment Compliance.** Compliance will be defined as described in Section 5.7. Each patient will be determined as compliant or non-compliant for each treatment component (capsules compliance and gel compliance). Treatment compliance rates based on active ingredient component will be summarized using proportions, and compliance rates will be compared between arms using Fisher's exact test. In addition, in order to determine whether compliance is different for capsule vs. gel administration, within-subject differences in treatment component compliance will be analyzed using the McNemar test among all patients, regardless of treatment arm.

**Subgroup analysis.** Exploratory analyses will be conducted by menopausal status (pre or peri-menopausal vs. post-menopausal). Descriptive statistics will be used to summarize study endpoints by group. In addition, linear regression models as described above will be used with the addition of menopausal status and possibly its interaction with treatment as predictors. Model-based linear contrasts will be constructed to test relevant treatment noninferiority or superiority hypotheses within subgroups. Similar analyses will be conducted in the subgroup of women with invasion in the post-treatment surgical sample.

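### Gel compliance is judged by canister weight without deducting gel the participant is told to waste, so the gel cut is slightly laxer than the capsule cut and the compliance comparisons tilt toward gel

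*Combined protocol and SAP*

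**What the plan says.** Section 5.7.1 sets one standard for both products: "Participants will be considered compliant if they have taken 80% of the prescribed doses", with a second condition of no more than three missed doses in the last 14 days before surgery.

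Section 5.7.3 says how the 80% is measured: "Capsule counts and weighing of gel dispensers will be performed at the conclusion of therapy". The capsule limit is D*80%, where D is the number of days between visits. The gel limit is 2D*80%*[m - sd(m)], where m and sd(m) "are the mean and standard deviation of the weight of one pump of the gel provided by the manufacturer". Neither value is given. The section adds that "Treatment compliance assessment will be based on the active ingredient component of the treatment regimen", meaning "the pill count for the Oral Tamoxifen group and gel dispenser weight for the 4-OHT gel group".

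The starting weight comes from the pharmacy at dispensing. Section 6.6 instructs: "Weigh all dispensers and record final gross weight".

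Appendix B, Gel application instructions, describes what happens next. At first use of a canister, "you must prime it by pressing the pump fully several times until gel is dispensed", with the spout pointed at a sink or wastebasket and the first dose not used. A mistaken double pump is discarded and pumped again. A new canister is started every 40 days. Study Diary Part II asks how many pumped doses were discarded, but neither section 5.7.3 nor 13.5.4 uses the answer.

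The resulting classification has three uses. Section 13.5.4 compares active-component compliance between arms by Fisher's exact test. It also states that "within-subject differences in treatment component compliance will be analyzed using the McNemar test among all patients", to learn whether compliance differs between capsule and gel. Sections 8.4.2 and 13.4.2 use compliance to form the per-protocol set.

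**The concern.** Weight lost since dispensing is the sum of gel applied, gel expelled in priming and gel discarded. Only the first is adherence. Capsules have no counterpart, because nobody is told to throw one away. A participant who uses both products on exactly the same days can therefore pass on gel and fail on capsules.

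The McNemar test is meant to answer whether women adhere better to a gel or to a capsule. The Fisher test sets gel weight in one arm against pill count in the other. If the measure leans toward gel, a small apparent advantage in adherence for the product under test could come from the measuring rule. The per-protocol set would also apply a different adherence standard in each arm.

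**Working it through.** **Inputs from the documents.** Two pumps a day (5.2). At least 80 reliable doses per canister (6.3.2). 88 g per pouch (6.6). 0.228% w/w, equal to 0.2% w/v (6.1). Treatment for 28 to 70 days (3.4). One canister up to day 40 and two after that (Appendix B).

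**Inputs assumed.** Wasted pumps per canister, w: the text guarantees 1, and 3 is shown as an illustration. The ratio s = sd(m)/m: 0, then 5%.

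**The plan's own figure.** 80 doses / 2 per day = 40 days, as stated. Density is 0.2/0.228 = 0.877 g/mL, so 88 g is about 100 mL, or about 100 pumps. That is some 20 more than the 80 reliable doses, so there is gel to spare for priming and discards.

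**Share of doses actually applied that just meets the weight rule**, with c canisters opened:

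cut = [2D × 0.8 × (1 - s) - w × c] / 2D

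With s = 0:

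| Days | Canisters | Limit in pumps | w = 1 | w = 3 | Capsules |
|---|---|---|---|---|---|
| 28 | 1 | 44.8 of 56 | 43.8/56 = 78.2% | 41.8/56 = 74.6% | 80% |
| 42 | 2 | 67.2 of 84 | 65.2/84 = 77.6% | 61.2/84 = 72.9% | 80% |
| 70 | 2 | 112 of 140 | 110/140 = 78.6% | 106/140 = 75.7% | 80% |

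For a participant with one breast at 28 days and w = 1, the cut is (22.4 - 1)/28 = 76.4%.

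**The sd(m) term.** It lowers the gel cut by a further 80% × s, which is 4 points at s = 5%. With w = 1 the cuts become 74.2%, 73.6% and 74.6%.

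**A case where classification changes (28 days, s = 0, w = 1).** A woman misses both products on the same 6 days, no more than 3 of them in the last 14 (counting a missed day as one dose). Gel: 22 × 2 + 1 = 45 pumps lost against 44.8, so she passes. Capsules: 22 against 22.4, so she fails.

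**Effect on the McNemar test.** A simulation gave 100 women identical day-by-day use of both products over 28 to 70 days, with the 14-day rule applied to both. Mean adherence was assumed to be 90%, 85% or 80%.

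| | Excess of gel over capsule compliance | McNemar rejections |
|---|---|---|
| w = 0, s = 0 | 0 | 0 |
| w = 1, s = 0 | 1.75, 2.98, 3.54 points | 0.5%, 8.7%, 13.2% |
| w = 3, s = 0 | 3.81, 6.97, 9.16 points | 17.8%, 70.7%, 92.2% |
| w = 0, s = 5% | 3.1, 5.64, 7.04 points | 9.8%, 49.7%, 72.7% |

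Every discordant pair favoured gel. When all pairs run one way, an exact two-sided test at an assumed 5% level rejects from 6 pairs on (2 × 0.5^6 = 0.031; 5 pairs give 0.0625). This is why a gap of 2 to 4 women per 100 seldom rejects and a gap of 9 usually does.

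**The case against.** - **Priming may waste little.** A reader might infer from the instruction to press several times that three to five full doses per canister are lost, putting the gel cut near 70%. The documents do not support that. Presses before gel appears remove little or no weight, and only the first dispensed dose is ordered to be left unused. Larger losses, and how often double pumps occur, are assumptions.
- **Section 5.7.3 speaks of gel consumed.** That could be read as net of waste, since the diary records discards. But the section states no deduction, and dispenser weight alone cannot supply one.
- **The 14-day rule is not weight-based.** This stands as a limit on the effect. A woman who misses 8 of 28 days (71% adherence) avoids failing it only if at least 5 of those misses fall in the first 14 days.
- **The sd(m) term is a deliberate allowance for pump variability.** That is fair, and it is a separate matter from priming. It still makes the two cuts unequal when gel and capsule are compared directly.
- **Lost capsules also count as taken.** True, but no instruction causes such losses.
- **A reader might infer that the per-protocol analysis favours gel on Ki-67.** The documents do not show this. A laxer cut keeps less adherent women in the gel arm. If adherence matters to Ki-67, that would dilute the gel effect and make non-inferiority harder to show.

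**Conclusion.** The mechanism and its direction follow from the text: read as written, section 5.7.3 counts gel thrown away on instruction as doses used. On what the documents guarantee, the effect is small. The gel cut sits 1.4 to 2.4 points below the capsule cut, about one treatment day. It would be 4.3 to 7.1 points below with an assumed three wasted pumps per canister. The sd(m) allowance adds to this by an amount that cannot be fixed without the manufacturer's figures.

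The McNemar and Fisher compliance comparisons are tilted modestly toward gel, and the per-protocol set applies unequal adherence cuts, with no demonstrated efficacy advantage for gel. The primary non-inferiority analysis is by intent to treat (8.4.2, 13.4.2, 13.8.1), so a reader should not infer that it or its power is affected. This is a minor point, worth correcting because the correction is cheap.

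**What to change.** In section 5.7.3, before the 80% rule is applied, subtract from the weight lost:

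1. a fixed priming allowance for each canister opened, of at least one pump times m; and
2. diary-recorded discards other than priming, times m.

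State in section 5.7.3 and in the diary that priming is not entered as a discard. Without that, priming can be deducted twice and the gel rule becomes the stricter one: at 28 days with w = 1, (44.8 + 1)/56 = 81.8%.

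Give the values of m and sd(m). For the McNemar and Fisher comparisons, use the same tolerance for both components, for example m without the sd(m) deduction. Otherwise the gel cut stays at 76% when s = 5%, even after the deductions. With both changes, and the true waste deducted, gel and capsules share the 80% cut.

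Confirm that the phone application, which may replace paper forms, records discards as the paper diary does.

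The cost is a few lines in sections 5.7.3 and 13.5.4 and one diary clarification. Canister first-use dates and paper-diary discards are already collected. The downside is reliance on self-reported discards and an assumed priming amount.
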